7.3. Subject Questionnaires

7.3.1. Fabry-Specific Pediatric Health and Pain Questionnaire

The FPHPQ includes questions about Fabry disease-specific symptoms (eg, sweating, pain, dizziness and tiredness, heat and cold intolerance, swollen eyelids, gastrointestinal symptoms, feeling thirsty, difficulty hearing, ringing, or buzzing noise in the ears, and ability and enjoyment to participate in sports). The frequency of these symptoms will be rated using a 5-point Likert scale (1=Always, 2=Often, 3=Sometimes, 4=Seldom, 5=Never). Pain severity is measured on an 11-point scale, numeric responses are given for onset of pain and school days missed, and yes/no questions are posed about difficulty hearing and other problems not specifically mentioned.

Descriptive summaries will be provided for the FPHPQ observed and change from baseline scores by visit and subgroup ie, sex (male, female), ERT status (ERT naïve, ERT 6+ months ago), and overall if feasible. Unscheduled visits will not be included. By-visit summary will also include the last post-baseline values.

A by-subject listing of FPHPQ scores will be provided.

7.3.2. Pediatric Quality of Life Inventory

The PedsQL[™] is a modular approach to measuring health-related quality of life in healthy children and adolescents and those with acute and chronic health conditions. It consists of 23 items and includes

questions about physical functioning (8 items), emotional functioning (5 items), social functioning (5 items), and school functioning (5 items) relative to the prior 7 days, using a 5-point scale (0=Never, 1=Seldom, 2=Sometimes, 3=Often, 4=Always). Both parents or legally-authorized representatives and subjects complete the appropriate version of the PedsQL[™] independently of one another. Parents or legally-authorized representatives and subjects may self-administer the questions after introductory instructions are given by study site personnel.

PedsQL[™] scoring procedure is as listed below:

Step 1: Transform Score:

Item scores are reversed and linearly transformed to a 0-100 scale as follows: 0=100, 1=75, 2=50, 3=25, 4=0.

Step 2: Calculate Scores:

Score by Dimensions:

- If more than 50% of the items in the scale are missing, the scores should not be computed.
- Mean score = Sum of the items over the number of items answered.
- Psychosocial Health Summary Score = Sum of the items over the number of items answered in the Emotional, Social, and School Functioning Scales;
- Physical Health Summary Score = Physical Functioning Score;
- Total Score: Sum of all the items over the number of items answered on all the scales.

Descriptive summary tables will be provided for the PedsQLTM observed and change from baseline of psychosocial, physical, and total scores by visit and subgroup, ie, sex (male, female), ERT status (ERT naïve, ERT experienced), and overall if feasible. By-visit summary will also include the last post-baseline values.

For both the teen report and the parent of teen report, a by-subject listing of PedsQLTM scores for each single question as well as psychosocial, physical, and total scores will be provided.

8. Analysis of Pharmacodynamics

8.1. Primary PD Endpoint and Analysis

The PD endpoint is change in plasma levels of lyso-Gb3. Descriptive summaries will be provided for the observed and change from baseline values to Month 6, and Month 12 by sex (male and female), ERT status (ERT naïve, ERT experienced), and overall based on the enrolled population.

A by-subject listing will also be provided.

9. Safety

The analysis population used for safety analyses will be the enrolled population. Safety will be assessed on the basis of extent of exposure, incidence of TEAEs, SAEs and AEs leading to discontinuation, clinical laboratory data, vital signs including body weight and height, ECG parameters, physical examinations, and Tanner stage.

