9. STUDY ASSESSMENTS AND PROCEDURES

The schedule of study assessments and procedures is presented in Table 2. Total blood volume to be drawn per subject is presented in Table 3.

All study assessments should be conducted by the investigator, and/or a suitably qualified designee. Information will be recorded in the source documents and, where appropriate, the eCRF.

All assessments that occur during the study, where applicable and to the extent possible, should be completed during the designated visit, preferably in the order specified below. Once established, every effort should be made to maintain the order of procedures at each study visit throughout the study.

Assessments	Baseline ^a	line ^a Treatment Period						EOT/ ET	Follow-up		
Visit Interval	Day 1	Month 3 (TC)	Month 6	Month 9 (TC)	Month 12	Month 15 (TC)	Month 18	Month 21 (TC)	Month 24		30-Day Safety
Visit Window (days)		±6	±6	±6	±6	±6	±6	±6	±6	±6	+6
Informed consent/assent	Х										
Inclusion/exclusion criteria	Х										
Medical history	Х										
Concomitant medications	Х	Х	X	X	Х	Х	X	X	X	Х	
Dosing diary ^b	Х	\rightarrow	\rightarrow	\rightarrow	X	\rightarrow	\rightarrow	\rightarrow	X		
FPHPQ questionnaire	Х		X		Х		X		X	Х	
PedsQL	Х		X		Х		X		X	Х	
Complete physical examination	X		Х		Х		Х		X	X	
Adverse events		Х	X	X	X	Х	X	X	X	X	X
Vital signs (BP, HR, RR, Temp)	X		X		Х		X		X	X	
Body weight	Х		X		X		X		X	X	
Height	Х		X		X		X		X	X	
Tanner Staging	Х		X		Х		X		X	Х	
12-lead ECG	Х		X		X		X		X	X	
Chemistry (including eGFR using Schwartz formula)	X		Х		Х		Х		X	Х	
Hematology	Х		X		Х		X		X	Х	

Table 2:Schedule of Assessments

19 August 2021 Confidential

Assessments	Baseline ^a	Treatment Period					EOT/ ET	Follow-up			
Visit Interval	Day 1	Month 3 (TC)	Month 6	Month 9 (TC)	Month 12	Month 15 (TC)	Month 18	Month 21 (TC)	Month 24		30-Day Safety
Visit Window (days)		±6	±6	±6	±6	±6	±6	±6	±6	±6	+6
Plasma lyso-Gb ₃ , analogs, and exploratory PD biomarkers	X		Х		X		Х		Х	Х	
Urinalysis (urine protein, albumin and microalbumin levels)	X		Х		X		Х		Х	Х	
Urine pregnancy test or date of LMP (as applicable) ^c	X	Х	Х	X	X	Х	Х	Х	Х	Х	Х
Echocardiogram (LVMi and additional parameters)	X				X				Х	Х	
Study treatment supply/resupply/ return	X		Х		Х		Х		Х	X ^d	

Table 2:Schedule of Assessments (Continued)

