Abbreviations: BP = blood pressure; ECG = electrocardiogram; eGFR = estimated glomerular filtration rate; EOT = end of treatment; ET = early termination; FPHPQ = Fabry-Specific Pediatric Health and Pain Questionnaire; HR = heart rate; LMP = last menstrual period; LVMi = left ventricular mass index; lyso-Gb₃ = globotriaosylsphingosine; PD = pharmacodynamic; PedsQL = Pediatric Quality of Life Inventory; RR = respiration rate; TC = telephone call; Temp = body temperature

Note: Following Month 24, visits will continue every 6 months with interim telephone contacts at 3-month intervals. The assessment schedule will repeat starting from Month 3.

Note: For the purposes of this study, a month is considered to be 30 days.

^a End of study assessments from Study AT1001-020 will be used as baseline assessments for Study AT1001-036.

^b A dosing diary will be completed throughout the treatment period.

^c Female subjects only; urine pregnancy tests will be conducted at each site visit. For menstruating females, date of LMP will be elicited during telephone contacts.

^d Return of study drug only.

Assessments	Baseline ^a	Month 6	Month 12	Total
Chemistry	4	4	4	12
Hematology	2	2	2	6
Plasma lyso-Gb ₃ and PD biomarkers	4	4	4	12
			Total:	30 mL

Table 3: Total Blood Volume to be Collected (as Scheduled) per Subject per Year

Abbreviations: lyso-Gb₃ = globotriaosylsphingosine; PD = pharmacodynamic

Note: Total collection volume does not take into account additional blood samples drawn during potential unscheduled visits.

^a End of study laboratory assessments for Study AT1001-020 will be used as Visit 1 assessments for Study AT1001-036. The blood volume from baseline assessments should not be counted for subsequent years.

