1.2. Timing of Analyses

The primary analysis of safety and efficacy and/or pharmacodynamics is planned after all subjects complete the final study visit or terminate early from the study. Unless otherwise specified, the analysis includes all data collected in the database through the time of the database lock.

2. Study Objectives and Endpoints

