2.1.2. Secondary Objectives

The secondary objectives of this study are as follows:

- to characterize the pharmacodynamics (PD) of migalastat in pediatric subjects diagnosed with Fabry disease and who have *GLA* variants amenable to treatment with migalastat
- to assess the efficacy of migalastat in pediatric subjects diagnosed with Fabry disease and who have *GLA* variants amenable to treatment with migalastat.

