5.1. General Summary Table and Individual Subject Data Listing Considerations

Summary tables and listings will have text (eg, headers or footers) providing explanatory notes that cover, as appropriate: date of data extraction, date of output generation, Statistical Analysis System (SAS®) program name, and any other output-specific details that require further elaboration.

The descriptive summary statistics will be prepared for baseline, each visit, and change from baseline to each visit (if appropriate).

Row entries in post text tables are made only if data exist for at least one subject (eg, a row with all zeroes will not appear). The only exception to this rule applies to tables that summarize the study termination status of subjects (eg, reasons for not completing the study). In this case, zeroes will appear for study termination reasons that no subject satisfied. The summary tables will clearly indicate the number of subjects to which the data apply and data that is unknown or not performed will be distinguished from missing data. All data collected will be reported in data listings.

Missing dates will be imputed as described in Section 5.7. Missing AE severity and relationship will be imputed as described in Section 5.7.2. No other missing data imputation will be performed. When imputed or derived data are included in the individual subject data listings, they will be flagged.

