5.6.1.5. Visit Windows

There will be no derivation for visit windows in terms of summary assessments. Nominal visits will be used for by-visit tables. For data with repeated observations at a given visit (eg, laboratory assessments), the earliest of the available non-missing values at a visit should be used in summary tables. Other observations will be considered as unscheduled visits.

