7.1. Laboratory Assessments

Efficacy analyses will include summaries of observed and change from baseline values for eGFR, urine protein, and urine albumin for scheduled visits by subgroup, ie, sex (male, female), ERT status (ERT naïve, ERT experienced), indicated in Section 4.6. By-visit summary will also include the last post-baseline values.

The eGFR will be calculated using the 2009 Schwartz formula for creatinine clearance.

A by-subject listing will be presented for each laboratory test.

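### SAP 8.1 names only Months 6 and 12 for the lyso-Gb3 summaries and has no last post-baseline row, although sampling continues to Month 24 and beyond

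*SAP*

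**What the plan says.** SAP 2.1.2 makes it a secondary objective "to characterize the pharmacodynamics (PD) of migalastat in pediatric subjects diagnosed with Fabry disease" with amenable variants. SAP 2.2.2 gives one PD endpoint, change from baseline in plasma lyso-Gb3. SAP 8.1 then sets the analysis: "Descriptive summaries will be provided for the observed and change from baseline values to Month 6, and Month 12 by sex", also by ERT status and overall, with a by-subject listing.

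The sampling row in Protocol Table 2 covers plasma lyso-Gb3, "analogs, and exploratory PD biomarkers". It is marked at baseline, Months 6, 12, 18 and 24, and EOT/ET; SAP Table 1 has the same row. A note to the table adds: "Following Month 24, visits will continue every 6 months with interim telephone contacts at 3-month intervals". The assessment schedule then repeats.

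Three general rules bear on the point:

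- SAP 5.1: "The descriptive summary statistics will be prepared for baseline, each visit, and change from baseline to each visit (if appropriate").
- SAP 1.2: "Unless otherwise specified, the analysis includes all data collected in the database through the time of the database lock".
- SAP 5.6.1.5, which derives no visit windows: "Nominal visits will be used for by-visit tables".

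Protocol 11.4.5 asks for descriptive statistics on lyso-Gb3 and names no time points.

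**The concern.** The study exists to follow subjects over the long term, and lyso-Gb3 is its only PD endpoint. Read as written, 8.1 stops the tabulated PD results at one year, while the efficacy and safety tables continue through every scheduled visit. A subject who leaves between scheduled visits also has the EOT/ET sample left out, even in the first year, because that sample is neither Month 6 nor Month 12 and no window rule moves it there. These values would appear only in the listing. What is at stake is the summary that shows whether the PD response is maintained. Two programmers could also build different tables from the same SAP.

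**Working it through.** The plan states no figure to reproduce. The check compares passages, with a short date calculation.

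**1. Time points.** The lyso-Gb3 row has five post-baseline marks: Months 6, 12, 18, 24 and EOT/ET. SAP 8.1 names 2 of these 5. Counting only fixed visits to Month 24, it names 2 of 4.

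**2. Last post-baseline row.** SAP 7.1 says: "By-visit summary will also include the last post-baseline values". An equivalent sentence stands in 7.2, 7.3.1, 7.3.2, 9.3, 9.4, 9.5, 9.6 and 9.7. That makes 9 of the 10 by-visit endpoint sections; the missing one is 8.1.

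**3. Is lyso-Gb3 summarised elsewhere?** No. SAP 7 covers the efficacy endpoints, and 9.3 covers hematology, serum chemistry and urinalysis.

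**4. Do the general rules override 8.1?**

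| Rule | Points towards | Qualifier |
|---|---|---|
| SAP 5.1 | every visit | only where appropriate |
| SAP 1.2 | all data to database lock | gives way to specific text |
| SAP 8.1 | Months 6 and 12 | none; specific to this endpoint |

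The endpoint-specific text is the unqualified one, so the general rules do not clearly prevail.

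**5. Could samples exist after Month 12?** Inputs: first enrolment estimated in Q4 2019 and last completion in Q2 2022 (Protocol Synopsis); a month is 30 days (Protocol 11.4). Longest possible follow-up of the earliest enrollee, in months = days / 30:

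- Shortest span, 31 Dec 2019 to 1 Apr 2022: 822 / 30 = 27.4. The last six-monthly visit reached is Month 24 (day 720).
- Longest span, 1 Oct 2019 to 30 Jun 2022: 1003 / 30 = 33.4. The last visit reached is Month 30 (day 900); Month 36 (day 1080) is out of range.

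By 19 August 2021, the date of the protocol version on which the SAP is based:

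- From 31 Dec 2019: 597 / 30 = 19.9.
- From 1 Oct 2019: 688 / 30 = 22.9.

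Both exceed Month 18 (18 × 30 = day 540). Samples after Month 12 were therefore foreseeable under that protocol version.

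**6. Is the limit deliberate?** Nothing says so. SAP 8.1 gives no reason, and SAP 12 declares only the change of analysis population. Other text looks carried over from a 12-month frame: SAP 9.4 lists Months 3, 6, 9 and 12, which fits the three-monthly visits before Amendment 2, and SAP 2.2.3 takes the echocardiogram endpoint to Month 12/ET where the protocol follows it over time. A leftover is a reasonable inference but is not proven.

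**The case against.** The best reply is that 8.1 does not say only Months 6 and 12. In SAP 5.1 the qualifier most naturally attaches to change from baseline, so observed values would be required at every visit without condition, and a programmer could satisfy 5.1 and 8.1 together. Protocol 11.4.5 sets no limit and SAP 12 declares no narrowing, so the SAP as a whole may not intend to stop at Month 12. The analysis is descriptive, PD is secondary to safety, and later values are listed in any case. Follow-up after Month 12 is inferred from estimated dates, and subjects may leave once reimbursed product is available, so later numbers could be very small or nil.

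Much of this stands as a limit on weight. The text does not prove that later data will be left out, and the dates show only that later visits are possible. It does not remove the conflict. Even on the favourable reading of 5.1, change from baseline stays qualified, and that is the PD endpoint itself. SAP 1.2 gives way to specific text, which 8.1 supplies. SAP 9.4 also lists months but retains both the each-visit wording and the last-value row; 8.1 has neither.

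**Conclusion.** The concern holds and should be fixed. It is an internal SAP conflict, not a departure from the protocol. Followed literally, 8.1 tabulates 2 of the 5 scheduled post-baseline points, stops at one year and leaves out EOT/ET values.

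The practical size is uncertain. Reaching Month 24 or Month 30 assumes that the protocol's estimated dates held and that the earliest enrollee stayed to the end. Entry is staggered and treatment duration varies, so those figures apply to the earliest enrollees only. The documents do not give actual follow-up, the number of subjects with samples after Month 12, or the PD sampling schedule before Amendment 2. No data are lost and no test is affected; what goes missing is the tabulated view of PD response over time.

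**What to change.** In SAP 8.1, replace the two named months with a rule along these lines: *Observed lyso-Gb3 and its change from baseline are summarised at every scheduled visit, including EOT/ET and any nominal visit at which PD samples were taken before Amendment 2, by sex, ERT status and overall, together with the last post-baseline value.* The pre-Amendment 2 clause applies only if such samples exist.

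If the limit to Months 6 and 12 is intended, give the reason and declare it in SAP 12, since the protocol sets no such limit.

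Two editorial edits can be made at the same time. In SAP 9.4, delete the month list and keep the each-visit wording. In SAP 2.2.3, word the echocardiogram endpoint as change over time, as the protocol does; SAP 7.2 already summarises echocardiography at each scheduled visit with the last value, so no echo table changes.

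The cost is one paragraph, two wording edits and a few more rows in the lyso-Gb3 table, with no new data collection. Rows after Month 12 may have small n, especially by sex and ERT status.

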9.1. Extent of Exposure and Drug Compliance

The duration of study drug exposure (in both days and months) and the number of doses of study drug exposure will be summarized for the enrolled population.

Duration of Exposure = end date of last dosing administration – start date of first dosing administration + 1Average Dose QOD = [Total dose received/ (Duration of exposure + 1)] * 2.

Drug Compliance (%) = Average Dose QOD/Planned Dose QOD (ie, 150 mg)

Drug Compliance will be summarized using descriptive summaries. The number and percentage of subjects with Drug Compliance <80%, $\ge80\%$ will be summarized.

A detailed listing of exposure to study drug and drug compliance will be presented.

9.2. Adverse Events

A TEAE is defined as any untoward medical occurrence in a subject or clinical investigation subject administered a pharmaceutical product and which does not necessarily have a causal relationship with this treatment and that begins on or after the date of the first dose of study drug in the 036 study.

Treatment-related TEAEs are defined as TEAEs that have an Investigator-defined relationship to treatment of "Definite", "Probable" or "Possible". Events with an investigator-defined relationship of "Unrelated" or "Unlikely Related" are considered as not related to treatment.

Serious TEAEs are defined as TEAEs that have a "yes" response to the eCRF question "Event Serious?". Serious adverse events are categorized as "Death", "Life-threatening", "Requires/Prolongs Hospitalization", "Disability/ Incapacity", "Congenital Anomaly/Birth Defect" or "Important Medical Event or Reaction".

An overall summary of TEAEs, will be tabulated, including the number and percentage of subjects reporting, by sex and overall:

- TEAEs
- Treatment-related TEAEs
- SAEs
- TEAEs leading to discontinuation of study drug
- TEAEs leading to death

The number of events and incidence rates will also be provided in the overall summary table. Incidence rate is calculated as: total events divided by the total patient years of exposure. Total patient years of exposure are the sum of the duration of exposure in years for all subjects.

Further, the following TEAE summaries will be provided by sex and overall:

- Any TEAEs by SOC and PT
- Any TEAEs by PT
- Treatment-related TEAEs by SOC and PT
- TEAEs by severity, by SOC and PT
- Serious TEAEs by SOC and PT
- Any non-serious TEAE by PT

When presenting summaries by SOC and PT, subjects are counted only once within each SOC and PT. TEAEs will be presented alphabetically by SOC and PT.

When presenting summaries by PT, subjects are counted only once in each PT. TEAEs will be presented in the order of descending frequency in the overall group.

When presenting summaries by severity, if a subject has more than one event within a given SOC or PT at different severities, the maximum severity will be tabulated. For example, if a subject had two events with the same PT, but one was moderate and the other severe, the severe TEAE will be included in the tabulation.

Subject listings will be provided for all AEs, TEAEs leading to discontinuation of study drug, TEAEs with an outcome of death, and SAEs.

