9.2.1. Medical History

Medical history will be collected by subject interview. Additionally, medical history deemed related to the subject's Fabry disease will be identified in the subject's medical records by the investigator or designee for entry into the appropriate eCRF, including, but not limited to such things as past serum creatinine results.

Since subjects will have participated in a previous migalastat study, historical medical history (ie, events or conditions that had their onset at least 90 days prior to Visit 1) will be considered as medical history for this study.

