10.1. Definitions

10.1.1. Adverse Event

An AE is defined as any untoward medical occurrence in a subject or clinical investigation subject administered a pharmaceutical product and which does not necessarily have a causal relationship with this treatment. An AE can therefore be any unfavorable and unintended sign, symptom, or disease temporally associated with the use of a medicinal product, whether or not considered related to the medicinal product.

Therefore, AEs include the following:

- The onset of new signs, symptoms, conditions, and illnesses
- Exacerbation of pre-existing conditions or illnesses
- Abnormal laboratory findings deemed clinically significant by the investigator
- Physical examination changes deemed clinically significant by the investigator
- Abnormal medical evaluation findings (eg, ECG) that are not documented at baseline and/or, in the investigator's opinion, represent a clinically significant change in the subject's health during study participation
 - Baseline medical evaluation findings (eg, ECG) that were not previously provided as medical history and can be determined as starting before baseline, are not considered AEs and will be recorded as medical history.

Adverse events will be recorded in the eCRF and subject's source record beginning from the time written consent (assent) is provided through the follow-up visit (at least 30 days after the last dose of study drug).

Subjects will be enrolling in this study following completion of Study AT1001-020. Therefore:

- Adverse events that are ongoing as of the last study visit of Study AT1001-020 will be entered in the AE eCRF.
 - The start date recorded in Study AT1001-020 will be the start date entered in the current study AE eCRF.
 - The event will be noted as continuing from Study AT1001-020 in the current study's AE eCRF.

A single diagnosis should be entered when known. If a clear diagnosis cannot be determined at the time of eCRF completion and the subject's source record entry, each sign and symptom must be recorded individually, until a final diagnosis is established. Conditions, signs, symptoms, etc that are present in the subjects' medical history at baseline should only be reported as AEs if they worsen (ie, increase in severity) since baseline.
Adverse events that begin after the first dose of investigational product in Study AT1001-036 will be considered treatment-emergent adverse events (TEAEs).

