- identifiable reporter

Additionally, the investigator's assessment of an event's relationship to study drug (see Section 10.2) is essential for Amicus to appropriately process the report and must be included.

Subjects and parents or legally-authorized representatives must be informed and understand that they should report events meeting the definition for SAE to study site personnel as soon as possible (and not wait until their next study visit).

If a non-serious event becomes serious, the change in status must be appropriately entered in the eCRF and the subject's source record, and reported to Amicus as described in Section 10.4.2.

If the investigator becomes aware of an SAE that occurs more than 30 days after the last dose of study drug, and considers the event possibly, probably, or definitely related to study drug, the investigator should contact the medical monitor (see Table 1) or the Clinical Operations Lead to determine how the SAE should be documented and reported.

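### The TEAE definition has no worsening clause, so a carried-over AT1001-020 event that worsens, becomes serious or turns fatal can drop out of the TEAE-based tables unless it is recorded as a new event

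*SAP*

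**What the plan says.** **Definition.** SAP 9.2 makes an adverse event treatment-emergent if it is one "that begins on or after the date of the first dose of study drug in the 036 study". Protocol 10.1.1 applies the same kind of test, except that it counts events starting after the first 036 dose where the SAP includes the day of that dose. Neither mentions an increase in severity, a change in seriousness or a fatal outcome.

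**Carried-over events.** Protocol 10.1.1 says: "Adverse events that are ongoing as of the last study visit of Study AT1001-020 will be entered in the AE eCRF". It adds: "The start date recorded in Study AT1001-020 will be the start date entered in the current study AE eCRF". The event is also marked as continuing from the earlier study.

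**Change in seriousness.** Protocol 10.1.2 says: "If a non-serious event becomes serious, the change in status must be appropriately entered in the eCRF and the subject's source record". It does not ask for a new record or a new onset date.

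**Other routes for worsening.** Protocol 10.1.1 includes the exacerbation of an existing condition in its list of what counts as an adverse event. It also says that conditions "present in the subjects' medical history at baseline should only be reported as AEs if they worsen", and explains worsening as greater severity. Protocol 9.2.1 takes as medical history "events or conditions that had their onset at least 90 days prior to Visit 1".

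**Displays.** In SAP 9.2 serious TEAEs are a subset of TEAEs. The tables by SOC and PT, by PT, by severity and by relationship, and the death row and death listing, are all limited to TEAEs. The overview has one row labelled simply SAEs, and there are listings of all AEs and of all SAEs.

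**The concern.** This is an extension in which subjects are meant to continue migalastat without a break (Protocol 9.1.2). Events that cross from AT1001-020 into 036 may therefore have begun on the drug. Whether such an event gets worse with further dosing is one of the main things a long-term safety study can show. Long-term safety is the primary objective, and the incidence of TEAEs and SAEs heads the list of safety endpoints (Protocol 11.1.1, SAP 2.2.3).

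A definition based on start date alone looks in the wrong place for this signal. An event that is mild at roll-over and later leads to hospitalization or death keeps an onset before 036 if its existing record is updated. It then has no place in the tables that readers of the study report will use. Two displays of serious events could also give different counts with nothing in the SAP to explain why.

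**Working it through.** No figure in the plan is at stake, so the check applies the rules case by case. The inputs are the TEAE test (SAP 9.2, Protocol 10.1.1), the carry-over rule (Protocol 10.1.1), the status-change rule (Protocol 10.1.2) and the date imputation (SAP 5.7.1).

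| Carried-over AT1001-020 event | Onset used | TEAE? | Where it appears |
|---|---|---|---|
| 1. Complete start date; severity increases; same record updated | 020 date | No | All-AE listing |
| 2. Complete start date; becomes serious; same record updated | 020 date | No | All-AE and SAE listings; SAEs row only if that row means all SAEs |
| 3. Complete start date; turns fatal; same record updated | 020 date | No | As case 2; absent from the TEAE-death row and the TEAE-death listing |
| 4. Worsening entered as a new event with a 036 onset | 036 date | Yes | All relevant TEAE displays |
| 5. Start day missing, same month and year as first 036 dose; or month missing, same year | Set to first-dose date, unless the stop date is earlier | Yes, changed or not | TEAE displays |
| 6. Start date wholly missing; stop date missing, or on or after first dose | None needed | Yes, changed or not | TEAE displays |

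In cases 1 to 3 each event contributes 0 to every SOC/PT, severity, treatment-related, serious-TEAE and TEAE-death display. In cases 4 to 6 it is counted.

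**Internal disagreement.** Take one case 2 event and no other serious event. The serious-TEAE table shows 0. The overview SAEs row shows 1 if it means all SAEs and 0 if it means serious TEAEs. The SAP does not say which.

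**Overlap with medical history.** Take an AT1001-020 event that began at least 90 days before Visit 1 and is still ongoing. Under Protocol 9.2.1 it is medical history. An increase in severity then makes it reportable as an adverse event, and it is a TEAE if dated from the worsening. Under the carry-over rule of Protocol 10.1.1 the same event goes on the adverse event form with its 020 date, and the same worsening on that record is not a TEAE. Nothing says which rule takes precedence.

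**Severity and seriousness.** The medical-history route is triggered by greater severity. Protocol 10.3 keeps severity separate from seriousness. An event that leads to hospitalization with its severity grade unchanged is therefore not clearly caught by that route either.

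**Protocol tables.** Protocol 11.4.4.2 plans SOC and preferred-term summaries of AEs without limiting them to TEAEs. SAP 9.2 limits them, and SAP Section 12 does not list this as a change. A wider AE table that would have shown cases 1 to 3 is thus not in the SAP.

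**The case against.** The strongest reply is that the Protocol already provides for worsening. Exacerbation of an existing condition is an adverse event in its own right under Protocol 10.1.1, so a site may enter a new event with a 036 onset, which is then a TEAE. Protocol 10.1.2 asks only that "the change in status must be appropriately entered in the eCRF"; it does not say that the old record must be kept, and it does not address greater severity or a fatal outcome. Protocol 10.4.1 leaves the recording detail to the eCRF Completion Guidelines, which are not among the documents. Older events may also be covered through medical history.

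This makes the point conditional but does not remove it. The provisions specific to carried-over events (original start date, marked as continuing, status change) point towards one updated record, and no text tells the site to open a second. Whether the event is counted then depends on site practice that the documents do not fix.

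Three stronger readings are tempting, and the documents do not support them:

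- A reader might infer that such events appear nowhere. They remain in the all-AE listing and, if serious, in the SAE listing. SAEs are named separately from TEAEs in the safety endpoint, so the overview SAEs row, read literally, would include them.
- A reader might infer that the TEAE rules always lower the count. Cases 5 and 6 run the other way: the imputation in SAP 5.7.1 can turn an unchanged carried-over event into a TEAE.
- A reader might attach a percentage. The documents give no planned number of subjects and no rate of worsening among carried-over events.

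**Conclusion.** The gap is real and should be closed. Both definitions test start date only, and the rules for carried-over events do not supply the missing clause. For events with a complete AT1001-020 start date whose existing record is updated, worsening, seriousness or death during 036 is left out of the SOC/PT, severity, treatment-related, serious-TEAE and TEAE-death displays. The loss is confined to displays restricted to TEAEs.

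The conclusion assumes that sites update the existing record; where they open a new one, the event is counted. Its size in subjects or events cannot be derived. What can be said is that each affected event counts as zero in those displays, and that the SAEs row and the serious-TEAE table may disagree.

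**What to change.** - **SAP 9.2 and Protocol 10.1.1:** define a TEAE as an adverse event that begins on or after the first 036 dose, or one with earlier onset that increases in severity, becomes serious or has a fatal outcome on or after that dose. Use the date of that change as the onset for analysis. The fatal-outcome limb is needed because an event already serious at roll-over could turn fatal with no new change in recorded severity or seriousness. Using one wording in both documents also removes the difference over the day of first dose.
- **Recording rule:** state that such a change opens a new adverse event record linked to the carried-over one, so that the date of change is captured.
- **SAP 9.2 overview:** state whether the SAEs row means all SAEs or serious TEAEs.
- **Protocol 9.2.1 and 10.1.1:** reconcile the two so that an event ongoing from AT1001-020 is not also entered as medical history.

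The cost is wording in both documents and a note in the form-completion guidelines, with possible queries to sites for subjects already enrolled. TEAE counts may be slightly higher. No new assessment is needed.
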